11 MEASUREMENT OF EFFECT

11.1 Antitumor Effect – Solid Tumors

For the purposes of this study, patients should be re-evaluated for response every 2 cycles. In addition to a baseline scan, confirmatory scans should also be obtained at least 4 weeks following initial documentation of objective response.

Response and progression will be evaluated in this study using the new international criteria proposed by the revised Response Evaluation Criteria in Solid Tumors (RECIST) guideline (version 1.1) [*Eur J Ca* 45:228-247, 2009]. Changes in the largest diameter (unidimensional measurement) of the tumor lesions and the shortest diameter in the case of malignant lymph nodes are used in the RECIST criteria.

11.1.1 Definitions

Evaluable for toxicity. All patients will be evaluable for toxicity from the time of their first treatment with study agents.

Evaluable for objective response. Only those patients who have measurable disease present at baseline, have received at least one cycle of therapy, and have had their disease re-evaluated will be considered evaluable for response. These patients will have their response classified according to the definitions stated below. (Note: Patients who exhibit objective disease progression prior to the end of cycle 1 will also be considered evaluable.)

Evaluable Non-Target Disease Response. Patients who have lesions present at baseline that are evaluable but do not meet the definitions of measurable disease, have received at least one cycle of therapy, and have had their disease re-evaluated will be considered evaluable for non-target disease. The response assessment is based on the presence, absence, or unequivocal progression of the lesions.

11.1.2 Disease Parameters

Measurable disease. Measurable lesions are defined as those that can be accurately measured in at least one dimension (longest diameter to be recorded) as ≥ 20 mm by chest x-ray, as ≥ 10 mm with CT scan, or ≥ 10 mm with calipers by clinical exam. All tumor measurements must be recorded in millimeters (or decimal fractions of centimeters).

Note: Tumor lesions that are situated in a previously irradiated area might or might not be considered measurable. *If the investigator thinks it appropriate to include them, the conditions under which such lesions should be considered must be defined in the protocol.*

Malignant lymph nodes. To be considered pathologically enlarged and measurable, a lymph node must be ≥ 15 mm in short axis when assessed by CT scan (CT scan slice

thickness recommended to be no greater than 5 mm). At baseline and in follow-up, only the short axis will be measured and followed.

Non-measurable disease. All other lesions (or sites of disease), including small lesions (longest diameter <10 mm or pathological lymph nodes with ≥ 10 to <15 mm short axis), are considered non-measurable disease. Bone lesions, leptomeningeal disease, ascites, pleural/pericardial effusions, lymphangitis cutis/pulmonitis, inflammatory breast disease, and abdominal masses (not followed by CT or MRI), are considered as non-measurable.

Note: Cystic lesions that meet the criteria for radiographically defined simple cysts should not be considered as malignant lesions (neither measurable nor non-measurable) since they are, by definition, simple cysts.

‘Cystic lesions’ thought to represent cystic metastases can be considered as measurable lesions, if they meet the definition of measurability described above. However, if non-cystic lesions are present in the same patient, these are preferred for selection as target lesions.

Target lesions. All measurable lesions up to a maximum of 2 lesions per organ and 5 lesions in total, representative of all involved organs, should be identified as **target lesions** and recorded and measured at baseline. Target lesions should be selected on the basis of their size (lesions with the longest diameter), be representative of all involved organs, but in addition should be those that lend themselves to reproducible repeated measurements. It may be the case that, on occasion, the largest lesion does not lend itself to reproducible measurement in which circumstance the next largest lesion which can be measured reproducibly should be selected. A sum of the diameters (longest for non-nodal lesions, short axis for nodal lesions) for all target lesions will be calculated and reported as the baseline sum diameters. If lymph nodes are to be included in the sum, then only the short axis is added into the sum. The baseline sum diameters will be used as reference to further characterize any objective tumor regression in the measurable dimension of the disease.

Non-target lesions. All other lesions (or sites of disease) including any measurable lesions over and above the 5 target lesions should be identified as **non-target lesions** and should also be recorded at baseline. Measurements of these lesions are not required, but the presence, absence, or in rare cases unequivocal progression of each should be noted throughout follow-up.

11.2 Methods for Evaluation of Measurable Disease

All measurements should be taken and recorded in metric notation using a ruler or calipers. All baseline evaluations should be performed as closely as possible to the beginning of treatment and never more than 4 weeks before the beginning of the treatment.

The same method of assessment and the same technique should be used to characterize each identified and reported lesion at baseline and during follow-up. Imaging-based evaluation is preferred to evaluation by clinical examination unless the lesion(s) being followed cannot be imaged but are assessable by clinical exam.

Clinical lesions Clinical lesions will only be considered measurable when they are superficial (e.g., skin nodules and palpable lymph nodes) and ≥ 10 mm diameter as assessed using calipers (e.g., skin nodules). In the case of skin lesions, documentation by color photography, including a ruler to estimate the size of the lesion, is recommended.

Chest x-ray Lesions on chest x-ray are acceptable as measurable lesions when they are clearly defined and surrounded by aerated lung. However, CT is preferable.

Conventional CT and MRI This guideline has defined measurability of lesions on CT scan based on the assumption that CT slice thickness is 5 mm or less. If CT scans have slice thickness greater than 5 mm, the minimum size for a measurable lesion should be twice the slice thickness. MRI is also acceptable in certain situations (e.g., for body scans).

Use of MRI remains a complex issue. MRI has excellent contrast, spatial, and temporal resolution; however, there are many image acquisition variables involved in MRI, which greatly impact image quality, lesion conspicuity, and measurement. Furthermore, the availability of MRI is variable globally. As with CT, if an MRI is performed, the technical specifications of the scanning sequences used should be optimized for the evaluation of the type and site of disease. Furthermore, as with CT, the modality used at follow-up should be the same as was used at baseline and the lesions should be measured/assessed on the same pulse sequence. It is beyond the scope of the RECIST guidelines to prescribe specific MRI pulse sequence parameters for all scanners, body parts, and diseases. Ideally, the same type of scanner should be used and the image acquisition protocol should be followed as closely as possible to prior scans. Body scans should be performed with breath-hold scanning techniques, if possible.

PET-CT At present, the low dose or attenuation correction CT portion of a combined PET-CT is not always of optimal diagnostic CT quality for use with RECIST measurements. However, if the site can document that the CT performed as part of a PET-CT is of identical diagnostic quality to a diagnostic CT (with IV and oral contrast), then the CT portion of the PET-CT can be used for RECIST measurements and can be used interchangeably with conventional CT in accurately measuring cancer lesions over time. Note, however, that the PET portion of the CT introduces additional data which may bias an investigator if it is not routinely or serially performed.

Ultrasound Ultrasound is not useful in assessment of lesion size and should not be used as a method of measurement. Ultrasound examinations cannot be reproduced in their entirety for independent review at a later date and, because they are operator dependent, it cannot be guaranteed that the same technique and measurements will be taken from one assessment to the next. If new lesions are identified by ultrasound in the course of the

study, confirmation by CT or MRI is advised. If there is concern about radiation exposure at CT, MRI may be used instead of CT in selected instances.

Tumor markers Tumor markers alone cannot be used to assess response. If markers are initially above the upper normal limit, they must normalize for a patient to be considered in complete clinical response. Specific guidelines for both CA-125 response (in recurrent ovarian cancer) and PSA response (in recurrent prostate cancer) have been published [*JNCI* 96:487-488, 2004; *J Clin Oncol* 17, 3461-3467, 1999; *J Clin Oncol* 26:1148-1159, 2008]. In addition, the Gynecologic Cancer Intergroup has developed CA-125 progression criteria which are to be integrated with objective tumor assessment for use in first-line trials in ovarian cancer [*JNCI* 92:1534-1535, 2000].

FDG-PET While FDG-PET response assessments need additional study, it is sometimes reasonable to incorporate the use of FDG-PET scanning to complement CT scanning in assessment of progression (particularly possible 'new' disease). New lesions on the basis of FDG-PET imaging can be identified according to the following algorithm:

- a. Negative FDG-PET at baseline, with a positive FDG-PET at follow-up is a sign of PD based on a new lesion.
- b. No FDG-PET at baseline and a positive FDG-PET at follow-up: If the positive FDG-PET at follow-up corresponds to a new site of disease confirmed by CT, this is PD. If the positive FDG-PET at follow-up is not confirmed as a new site of disease on CT, additional follow-up CT scans are needed to determine if there is truly progression occurring at that site (if so, the date of PD will be the date of the initial abnormal FDG-PET scan). If the positive FDG-PET at follow-up corresponds to a pre-existing site of disease on CT that is not progressing on the basis of the anatomic images, this is not PD.
- c. FDG-PET may be used to upgrade a response to a CR in a manner similar to a biopsy in cases where a residual radiographic abnormality is thought to represent fibrosis or scarring. The use of FDG-PET in this circumstance should be prospectively described in the protocol and supported by disease-specific medical literature for the indication. However, it must be acknowledged that both approaches may lead to false positive CR due to limitations of FDG-PET and biopsy resolution/sensitivity.

Note: A 'positive' FDG-PET scan lesion means one which is FDG avid with an uptake greater than twice that of the surrounding tissue on the attenuation corrected image.

11.3 Response Criteria

11.3.1 Evaluation of Target Lesions

Response and progression will be evaluated using RECIST version 1.1. Changes in the largest diameter (unidimensional measurement) of the tumor lesions and the shortest diameter in the case of malignant lymph nodes are used in the RECIST criteria per [Section 11.1](#).

Complete Response (CR): Disappearance of all target lesions. Any pathological lymph nodes (whether target or non-target) must have reduction in short axis to <10 mm.

Partial Response (PR): At least a 30% decrease in the sum of the diameters of target lesions, which is based on the long axis for non-nodal lesions and the short axis for nodal lesions of target lesions, taking as reference the baseline sum diameters.

Progressive Disease (PD): At least a 20% increase in the sum of the diameters of target lesions, which is based on the long axis for non-nodal lesions and the short axis for nodal lesions of target lesions, taking as reference the smallest sum on study (this includes the baseline sum if that is the smallest on study). In addition to the relative increase of 20%, the sum must also demonstrate an absolute increase of at least 5 mm. (Note: the appearance of one or more new lesions is also considered progressions).

Stable Disease (SD): Neither sufficient shrinkage to qualify for PR nor sufficient increase to qualify for PD, taking as reference the smallest sum diameters while on study.

11.3.2 Evaluation of Non-Target Lesions

Complete Response (CR): Disappearance of all non-target lesions and normalization of tumor marker level. All lymph nodes must be non-pathological in size (<10 mm short axis). Note: If tumor markers are initially above the upper normal limit, they must normalize for a patient to be considered in complete clinical response.

Non-CR/Non-PD: Persistence of one or more non-target lesion(s) and/or maintenance of tumor marker level above the normal limits.

Progressive Disease (PD): Appearance of one or more new lesions and/or *unequivocal progression* of existing non-target lesions. *Unequivocal progression* should not normally trump target lesion status. It must be representative of overall disease status change, not a single lesion increase.

Although a clear progression of “non-target” lesions only is exceptional, the opinion of the treating physician should prevail in such circumstances, and the progression status should be confirmed at a later time by the review panel (or Principal Investigator).

11.3.3 Evaluation of Best Overall Response

The best overall response is the best response recorded from the start of the treatment until disease progression/recurrence (taking as reference for progressive disease the smallest measurements recorded since the treatment started). The

patient's best response assignment will depend on the achievement of both measurement and confirmation criteria.

For Patients with Measurable Disease (i.e., Target Disease)

Target Lesions	Non-Target Lesions	New Lesions	Overall Response	Best Overall Response when Confirmation is Required*
CR	CR	No	CR	>4 wks. Confirmation**
CR	Non-CR/Non-PD	No	PR	>4 wks. Confirmation**
CR	Not evaluated	No	PR	
PR	Non-CR/Non-PD/not evaluated	No	PR	
SD	Non-CR/Non-PD/not evaluated	No	SD	documented at least once >4 wks. from baseline**
PD	Any	Yes or No	PD	no prior SD, PR or CR
Any	PD***	Yes or No	PD	
Any	Any	Yes	PD	

* See RECIST 1.1 manuscript for further details on what is evidence of a new lesion.
 ** Only for non-randomized trials with response as primary endpoint.
 *** In exceptional circumstances, unequivocal progression in non-target lesions may be accepted as disease progression.

Note: Patients with a global deterioration of health status requiring discontinuation of treatment without objective evidence of disease progression at that time should be reported as “symptomatic deterioration.” Every effort should be made to document the objective progression even after discontinuation of treatment.

For Patients with Non-Measurable Disease (i.e., Non-Target Disease)

Non-Target Lesions	New Lesions	Overall Response
CR	No	CR
Non-CR/non-PD	No	Non-CR/non-PD*
Not all evaluated	No	not evaluated
Unequivocal PD	Yes or No	PD
Any	Yes	PD

* ‘Non-CR/non-PD’ is preferred over ‘stable disease’ for non-target disease since SD is increasingly used as an endpoint for assessment of efficacy in some trials so to assign this category when no lesions can be measured is not advised

11.4 Duration of Response

Duration of overall response: The duration of overall response is measured from the time measurement criteria are met for CR or PR (whichever is first recorded) until the first date that recurrent or progressive disease is objectively documented (taking as reference for progressive disease the smallest measurements recorded since the treatment started).

The duration of overall CR is measured from the time measurement criteria are first met for CR until the first date that progressive disease is objectively documented.

Duration of stable disease: Stable disease is measured from the start of the treatment until the criteria for progression are met, taking as reference the smallest measurements recorded since the treatment started, including the baseline measurements.

11.5 Confirmatory Measurement

To be assigned a status of PR or CR, changes in tumor measurements must be confirmed by repeat assessments that should be performed at least 4 weeks after the criteria for response are first met. In the case of SD, follow-up measurements must have met the SD criteria at least once after study entry for a minimum interval of 8 weeks.

12 DATA REPORTING / REGULATORY REQUIREMENTS

Adverse event lists, guidelines, and instructions for AE reporting can be found in [Section 7.0](#) (Adverse Events: List and Reporting Requirements).

12.1 Data Reporting

12.1.1 Method

Data will be collected in the Center for Cancer Research C3D database. This study will be monitored by the Clinical Data Update System (CDUS) Version 3.0. Cumulative protocol- and patient-specific CDUS data will be submitted electronically to CTEP on a quarterly basis, either by FTP burst of data or via the CDS web application. Reports are due January 31, April 30, July 31, and October 31. Instructions for submitting data using the CDUS can be found on the CTEP Web site (<http://ctep.cancer.gov/reporting/cdus.html>).

Note: All adverse events that have occurred on the study, including those reported through CTEP-AERS, must be reported via the monitoring method identified above.

12.1.2 Responsibility for Data Submission

N/A

12.2 CTEP Multicenter Guidelines

N/A

12.3 Collaborative Agreements Language

The agent(s) supplied by CTEP, DCTD, NCI used in this protocol is/are provided to the NCI under a Collaborative Agreement (CRADA, CTA, CSA) between the Pharmaceutical Company(ies) (hereinafter referred to as “Collaborator(s)”) and the NCI Division of Cancer

Treatment and Diagnosis. Therefore, the following obligations/guidelines, in addition to the provisions in the “Intellectual Property Option to Collaborator” (http://ctep.cancer.gov/industryCollaborations2/intellectual_property.htm) contained within the terms of award, apply to the use of the Agent(s) in this study:

- 12.3.1** Agent(s) may not be used for any purpose outside the scope of this protocol, nor can Agent(s) be transferred or licensed to any party not participating in the clinical study. Collaborator(s) data for Agent(s) are confidential and proprietary to Collaborator(s) and shall be maintained as such by the investigators. The protocol documents for studies utilizing Agents contain confidential information and should not be shared or distributed without the permission of the NCI. If a copy of this protocol is requested by a patient or patient’s family member participating on the study, the individual should sign a confidentiality agreement. A suitable model agreement can be downloaded from: <http://ctep.cancer.gov>.
- 12.3.2** For a clinical protocol where there is an investigational Agent used in combination with (an)other Agent(s), each the subject of different Collaborative Agreements, the access to and use of data by each Collaborator shall be as follows (data pertaining to such combination use shall hereinafter be referred to as "Multi-Party Data"):
- a. NCI will provide all Collaborators with prior written notice regarding the existence and nature of any agreements governing their collaboration with NCI, the design of the proposed combination protocol, and the existence of any obligations that would tend to restrict NCI's participation in the proposed combination protocol.
 - b. Each Collaborator shall agree to permit use of the Multi-Party Data from the clinical trial by any other Collaborator solely to the extent necessary to allow said other Collaborator to develop, obtain regulatory approval or commercialize its own Agent.
 - c. Any Collaborator having the right to use the Multi-Party Data from these trials must agree in writing prior to the commencement of the trials that it will use the Multi-Party Data solely for development, regulatory approval, and commercialization of its own Agent.
- 12.3.3** Clinical Trial Data and Results and Raw Data developed under a Collaborative Agreement will be made available to Collaborator(s), the NCI, and the FDA, as appropriate and unless additional disclosure is required by law or court order as described in the IP Option to Collaborator (http://ctep.cancer.gov/industryCollaborations2/intellectual_property.htm). Additionally, all Clinical Data and Results and Raw Data will be collected, used and disclosed consistent with all applicable federal statutes and regulations for the protection of human subjects, including, if applicable, the Standards for Privacy of Individually Identifiable Health Information set forth in 45 C.F.R. Part 164.

- 12.3.4** When a Collaborator wishes to initiate a data request, the request should first be sent to the NCI, who will then notify the appropriate investigators (Group Chair for Cooperative Group studies, or PI for other studies) of Collaborator's wish to contact them.
- 12.3.5** Any data provided to Collaborator(s) for Phase 3 studies must be in accordance with the guidelines and policies of the responsible Data Monitoring Committee (DMC), if there is a DMC for this clinical trial.
- 12.3.6** Any manuscripts reporting the results of this clinical trial must be provided to CTEP by the Group office for Cooperative Group studies or by the principal investigator for non-Cooperative Group studies for immediate delivery to Collaborator(s) for advisory review and comment prior to submission for publication. Collaborator(s) will have 30 days from the date of receipt for review. Collaborator shall have the right to request that publication be delayed for up to an additional 30 days in order to ensure that Collaborator's confidential and proprietary data, in addition to Collaborator(s)'s intellectual property rights, are protected. Copies of abstracts must be provided to CTEP for forwarding to Collaborator(s) for courtesy review as soon as possible and preferably at least three (3) days prior to submission, but in any case, prior to presentation at the meeting or publication in the proceedings. Press releases and other media presentations must also be forwarded to CTEP prior to release. Copies of any manuscript, abstract and/or press release/ media presentation should be sent to:
E-mail: [REDACTED]

The Regulatory Affairs Branch will then distribute them to Collaborator(s). No publication, manuscript or other form of public disclosure shall contain any of Collaborator's confidential/ proprietary information.

13 STATISTICAL CONSIDERATIONS

13.1 Study Design/Endpoints

A primary objective of the trial is to establish the safety, tolerability, and MTD of the combination. Another primary objective is to evaluate changes in MET and phospho-MET following treatment with pazopanib and ARQ 197.

Twelve patients will be treated initially in Cohort A. Mean increases in MET and pMET in these 12 patients will be measured to assess whether or not it is statistically significant.

13.2 Sample Size/Accrual Rate

The study is designed to have 5 dose escalation cohorts, with a standard design using 3 patients per cohort, unless DLT is noted, in which case up to 6 patients may be enrolled in a cohort. With 6 dose levels, up to 36 patients may be enrolled for determination of the MTD. In addition, to

characterizing the pharmacodynamics of the combination, up to an additional 12 patients will be enrolled in the expansion phase, for a total of 54 patients. Only patients with paired tumor biopsies will be considered evaluable in the expansion phase. To allow for a few patients who may not be evaluable, the accrual ceiling will be set at 56 patients.

It is anticipated that 2-3 patients per month may be enrolled onto this trial. Thus, depending on the number of patients needed to reach the MTD, it is expected that 18 to 27 months will be required to accrue the number of patients necessary to complete the trial.

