- Establish the maximum tolerated dose (MTD) of the combination of pazopanib with ARQ 197 in patients with refractory advanced solid tumors.
- Evaluate changes in MET and phospho-MET following treatment with pazopanib and ARQ 197 in patients with refractory advanced solid tumors.
- Determine the pharmacokinetics (PK) of pazopanib and ARQ 197.
- Determine and compare levels of total MET, phospho MET, HIF-1 α , and epithelial-mesenchymal transition markers (e-cadherin, beta catenin) in tumor biopsy samples prior to and following administration of the study drugs.
- Determine and compare levels of circulating levels of HGF, soluble MET (sMET), VEGF-A, and soluble VEGFR2 (sVEGFR2) prior to and following administration of the study drugs.
- Determine polymorphisms in the CYP2C19 and correlate these with the observed toxicities, and the PK of ARQ 197.
- Evaluate antitumor activity of the combination of pazopanib and ARQ 197 in patients with refractory advanced solid tumors.

[figure not shown]
Eligibility:

- Adults with advanced, refractory solid tumors. Patients enrolling in the expansion cohorts must have advanced sarcoma, gastric cancer, and MET-expressing malignancies, have disease amenable to biopsy, and be willing to undergo pre-and post-treatment biopsies.

Study Design:

[figure not shown]
- ARQ 197 will be administered orally twice daily and pazopanib orally once daily, in 28-day cycles.
- Dose escalation will proceed using the traditional 3+3 design.
- Once the MTD is established, an additional cohort will be accrued for pharmacodynamic (PD) studies in tumor biopsies (required in the expansion phase). For the first week, patients will receive pazopanib alone to compare PK and PD results; combination therapy will be given from week 2 onwards.

SCHEMA: DOSE ESCALATION PHASE

- ^a Pazopanib (P) po q day and ARQ 197 (A) po bid continuously throughout in patients on the dose escalation phase. Pazopanib will be taken on an empty stomach 1 hour before a meal and ARQ 197 will be taken with food.
- ^b Tumor biopsies (optional during the dose escalation phase) will be performed at baseline (pre-treatment) and on C1D8, 8-12 hours after the Day 7 evening dose of ARQ 197 (taken 1 hour after pazopanib).
- ^c Blood samples for PD analyses collected at baseline (pre-treatment), on C1D1 (2, 4, and 6 hours after pazopanib), on C1D15 (pre-study drug administration), and on C2D1 (pre-study drug administration).

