5.1.2 Expansion Phase

Once the MTD is established, an additional cohort of patients will initially be treated with pazopanib alone, and tumor biopsies will be obtained to assess target inhibition, as outlined below. Tumor biopsies will be mandatory during the expansion phase of the study. Biopsies will be obtained at the time points outlined below. Depending on the results obtained from the tumor biopsies in the first few patients, the timing of the biopsy can be adjusted, but the number of tumor biopsies and the procedure will not change. Any change in the timing of the tumor biopsy will be discussed with the patient prior to obtaining informed consent.

The cohort and dosing regimens after establishment of the MTD are described below. When administered as a single agent during the expansion phase, the dose of pazopanib will correspond to the dose determined for the combination MTD if the MTD is determined at dose level 5 (ARQ 197 360 mg BID/pazopanib 800 mg QD) or 6 (ARQ 197 360 mg BID/pazopanib 600 mg QD). Otherwise, the dose of pazopanib will be determined after discussion with CTEP. Once the MTD is established, the data will be discussed with CTEP prior to proceeding with accrual for the expansion phase.

Cohort A (12 patients): Pazopanib will be given once daily as single agent from cycle 1 day 1 to day 7. Tumor biopsy will be done before drug administration on study (baseline) and on cycle 1 day 8, 8-12 hours after pazopanib administration. **After** the tumor biopsy, patients will start to receive ARQ 197 in addition to pazopanib at the combination MTD.

Twelve evaluable patients with both pre- and post-treatment biopsies will be treated initially in Cohort A. Mean increases in MET and pMET in these 12 patients will be measured to assess whether or not they are statistically significant.

For the purposes of final analysis of the expansion phase, only patients with paired tumor biopsies will be considered evaluable. Patients with fewer than the 2 required biopsies will not be considered evaluable for the expansion phase and will need to be replaced in the accrual scheme of the expansion phase. If a patient has a dose-limiting toxicity (DLT) with the single lead-in agent pazopanib in the expansion cohort, the patient will be taken off treatment.

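### Section 13.2 gives a total of 54 patients, but its own components, up to 36 plus up to 12, add to 48

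*Combined protocol and SAP*

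**What the plan says.** Section 13.2 builds the sample size in three steps.

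- Escalation: "With 6 dose levels, up to 36 patients may be enrolled for determination of the MTD". The same section allows up to six patients in a cohort when a DLT is seen.
- Expansion and total: "up to an additional 12 patients will be enrolled in the expansion phase, for a total of 54 patients".
- Allowance: "To allow for a few patients who may not be evaluable, the accrual ceiling will be set at 56 patients".

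On timing it says "It is anticipated that 2-3 patients per month may be enrolled onto this trial" and, "depending on the number of patients needed to reach the MTD, it is expected that 18 to 27 months will be required".

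Other sections give the same components. Table 2 in Section 5.1.1 lists levels 1 to 5 and a level 6 that is used only if level 5 proves to be above the MTD. The Précis describes a single expansion cohort: "Once the MTD is established, an additional cohort will be accrued for pharmacodynamic (PD) studies in tumor biopsies". Section 5.1.2 sets its size: "Twelve evaluable patients with both pre- and post-treatment biopsies will be treated initially in Cohort A". Section 13.1 also gives twelve.

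**The concern.** The sentence that states the total also states one of its two components, and the sentence before it states the other. Both are maxima, yet the total exceeds their sum. A reader cannot tell whether 48 or 54 patients are planned before replacements.

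Two other figures are read against that total. One is the accrual time, which may have been computed from the unreconciled number. The other is the room under the ceiling for patients who do not count. That room is relevant because Sections 5.1.2 and 9.1.2.2 require expansion patients without paired biopsies to be replaced, and Section 9.1.2.2 lets patients decline later biopsies. Section 5.1.1 also sets conditions under which an escalation patient counts towards dose decisions.

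**Working it through.** **Inputs.** Six dose levels, up to 6 patients per level, up to 36 in escalation, up to 12 in expansion, total 54, ceiling 56, and 2 to 3 patients per month (all Section 13.2). Twelve in Cohort A (Sections 5.1.2 and 13.1). Table 2 (Section 5.1.1) has eight rows: levels 1 to 6, -1 and -2.

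**Escalation.** 6 × 6 = 36, which reproduces the plan's figure.

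**Total.** 36 + 12 = 48. The plan's 54 is not reproduced. The difference is 54 − 48 = 6, or 6/48 = 12.5% of the sum of the components.

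**Other readings of the stated inputs.**

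| Reading | Sum |
|---|---|
| 5 levels × 6, plus 12 | 42 |
| 6 levels × 6, plus 12 | 48 |
| 8 levels × 6 (all rows of Table 2), plus 12 | 60 |

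None gives 54.

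**What would give 54.** 42 + 12 (seven levels), 36 + 18 (a larger expansion) or 30 + 24 (five levels and an expansion of 24). None of these pairs is stated in the documents.

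**Accrual time.** Patients divided by the monthly rate:

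| Patients | At 3 per month | At 2 per month |
|---|---|---|
| 48 | 16 months | 24 months |
| 54 | 18 months | 27 months |
| 56 | 18.7 months | 28 months |

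The stated 18 to 27 months matches 54 exactly. That it was computed from 54 is an inference, because the text makes the duration depend on how many patients are needed to reach the MTD.

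**Places left under the ceiling.** 56 − 54 = 2; 56 − 48 = 8.

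**The case against.** The strongest objection is about weight. The working limit on enrolment is the ceiling of 56, and both 48 and 54 lie below it. Escalation cohorts are governed by Section 5.1.1 and the expansion size by Section 5.1.2, so nothing that happens to a patient and no inference turns on the 54. This stands, and it limits the point to the stated sample size and accrual time.

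Several possible explanations for the extra 6 were considered.

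- **Non-evaluable patients.** Section 13.2 provides for them after the total, through the ceiling. Counting them within 54 as well would count them twice.
- **More than six at a level.** The escalation table in Section 5.1.1 sets a minimum of three further patients after one DLT in three, so six is not a strict cap there. Section 13.2, however, uses six per cohort and 36 overall, and the looser wording does not yield 54.
- **A later expansion stage.** Sections 5.1.2 and 13.1 describe the twelve as the patients treated at first, which could hint at more. No later stage or number is given, and Section 13.2 treats 12 as the maximum.
- **Five cohorts or six levels.** Section 13.2 opens with five escalation cohorts and then uses six levels. The conditional level 6 accounts for this, and five levels moves the sum further away, to 42.
- **A total carried over.** Section 2.4.1.1 records that expansion cohorts were cut by amendment, so an old total may have survived. This is plausible but unproven, because the former cohort sizes are not given.

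It can also be said that 18 to 27 months is only an expectation and lies within the 16 to 28 months spanned by 48 to 56 patients. That is right: the duration needs a recheck and is not shown to be wrong.

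**Conclusion.** The concern holds. The stated total exceeds the sum of its stated components by 6 patients (54 against 48), and no reading of the documents' own inputs gives 54. The conclusion rests only on addition within Section 13.2, with the expansion size confirmed in Sections 5.1.2 and 13.1 and the six levels in Table 2. Which figure is wrong cannot be settled from the documents, although the Précis and Sections 5.1.2 and 13.1 all favour one expansion cohort of 12.

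The correction should be made because the sample-size section contradicts itself, but its reach is small: the planned total, the likely basis of the accrual time, and whether 8 or 2 places are held for non-evaluable patients. Escalation rules, cohort sizes and analyses are unaffected.

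**What to change.** Reconcile the total with its components in Section 13.2. On the components as written, the total becomes 36 + 12 = 48. If 54 is intended, correct whichever component produces it and make Sections 5.1.1, 5.1.2, 13.1 and 13.2 agree. In the same edit, explain that the sixth level is the conditional one, so that five cohorts and six levels do not read as a second conflict.

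Then recheck the accrual time against the reconciled total: 16 to 24 months for 48 patients, or about 19 to 28 months at the ceiling. State how many places under the ceiling are meant for non-evaluable patients. The ceiling of 56 need not change. The cost is protocol wording only.
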